7.2. Adverse and Serious Adverse Events

Safety assessments will consist of recording all AEs and SAEs, protocol-specified hematology and clinical chemistry variables, clinical examination findings, measurement of protocol-specified vital signs, and the results from other protocol-specified tests that are deemed critical to the safety evaluation of voxelotor.

All AEs will be recorded from the time the study participant signs the ICF until at least 28 days after last dose of study drug or EOS visit (per Appendix 1). The determination, evaluation, reporting, and follow-up of AEs will be performed as outlined in this section. At each visit, the study participant will be asked about any new or ongoing AE since the previous visit. Assessments of AEs will occur at each study visit.

Clinically significant changes from study baseline in physical examination findings, weight, vital signs, and clinical laboratory parameters, will be recorded as AEs or SAEs, as appropriate.

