15. APPENDICES

Appendix 1. Schedule of assessments

Assessments			Tre	eatment I	Period					End of Studyi
Study Day(s)	Day 1ª	W4* ± 5 days	W8* ± 5 days	W12 ± 5 days	W24 ± 10 days	W36 ± 10 days	W48 ± 10 days	Q12 Wks ± 10 days	Q24 Wks ± 10 days	
Informed Consent/Assent	X							unjs	unjs	
Eligibility Assessment	X									
Medical History	X									
Physical Examination b	X	X	X	X	X		X		X	X
Vital Signs ^c	X	X	X	X	X		X			X
Adverse Events	X	X	X	X	X		X		X	X
Concomitant Medications	X	X	X	X	X		X		X	X
Hematology/Chemistry analyzed by Central Laboratory (US and Europe only) ^d	X	X	X	X	X		X			X
Hematology/Chemistry analyzed by Local Laboratory (ex-US and ex-Europe only) ^{d, e}	Xª	X	X	X	X		X		X f	Х
Exploratory Laboratory CCI (US and Europe Only)	X			X	X		X			
Urine Pregnancy Test ^g	X	X	X	X	X		X		X	X
Drug Dispensing and Accountability ^h	X			X	X	X	X	X	X	Х

Assessments		Treatment Period							End of Studyi	
Study Day(s)	Day	W4*	W8*	W12	W24	W36	W48	Q12	Q24	
	1ª	± 5	± 5	± 5	± 10	± 10	± 10	Wks	Wks	
		days	days	days	days	days	days	± 10	± 10	
								days	days	

Amendment 3

Abbreviations: Q = every; W = week; Wks = weeks

- * Participants from GBT440-031 who received GBT440 900 mg or placebo, or who received voxelotor for less than 12 weeks will have additional assessments at Week 4 and Week 8.
- a. Eligibility assessments will be determined on Day 1 prior to dosing. If labs were done for GBT440-031 or this study within 7 days of Day 1, they do not need to be repeated on Day 1.
- Abbreviated Physical Exam which includes: general appearance, examination of eyes, skin, cardiovascular and respiratory systems, an abdominal examination and a symptom directed examination.
- c. Vital signs (heart rate [HR], blood pressure [BP]) will be collected after a participant has rested for at least 5 minutes in the seated or supine position. A repeated measurement of HR and BP will be taken if the first reading is outside the normal range and deemed clinically significant.
- d. Hematology assessments will include: red blood cell (RBC), hematocrit (Hct), hemoglobin (Hb), platelets, white blood cell (WBC), we reticulocytes, absolute reticulocytes, RBC distribution width (RDW), mean corpuscular volume (MCV) and mean corpuscular hemoglobin concentration (MCHC). After Week 48, hematology assessments should only be performed per standard of care.

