- e. Serum chemistries will include: Alanine aminotransferase (ALT), alkaline phosphatase (ALK), aspartate aminotransferase (AST), bicarbonate, BUN, creatinine, LDH, sodium, potassium, bilirubin (total, direct, and indirect). After Week 48, serum chemistries should only be performed per standard of care.
- f. After Week 48 (for participants enrolled outside of the United States and Europe), laboratory values for measures of hemolysis such as hemoglobin, % reticulocytes, absolute reticulocytes, and bilirubin (total, direct, and indirect) will be collected every 24 weeks.
- g. If a urine pregnancy test is positive, the result must be confirmed per local standard of care (eg. ultrasound or serum pregnancy test).
- h. Voxelotor will be dispensed in 12-week (~90 day) intervals with instruction to participants to return any used/unused bottles to clinic.
- The End of Study (EOS) visit should be conducted within 28-35 days after last dose of study drug for participants who withdraw from the study early.

The EOS visit can occur any time after participants obtains commercial voxelotor for participants who complete study per protocol. Participants who complete study per protocol should remain on study drug until EOS visit is completed.

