#### 3.2. Visit Windows

For summaries by timepoint (e.g., laboratory values and vital signs), analysis visit windows will be used to classify assessments based on the actual treatment day of the measurement regardless of the original nominal visit label. This includes assessments collected at Unscheduled or EOS visits. Target study days, the protocol-specified study day windows, and the analysis visit windows are shown in Table 1.

**Table 1:** Analysis Windows

Timepoint	Target Study Day (relative to first dose)	Visit Window per Protocol (treatment days)	Window for Statistical Analysis (treatment days)
Baseline	1		Last value a taken on or prior to date of first dose in GBT440-034
Week 4	28	[23, 33]	[2, 42]
Week 8	56	[51, 61]	[43, 70]

Timepoint	Target Study Day (relative to first dose)	Visit Window per Protocol (treatment days)	Window for Statistical Analysis (treatment days)		
Week 12	84	[79, 89]	[71, 126]		
Week 24	168	[158, 178]	[127, 252]		
Week 48	336	[326, 346]	[253, 420]		
Week 72	504	[494, 514]	[421, 588]		
Week 96	672	[662, 682]	[589, 756]		
Week 120	840	[830, 850]	[757, 924]		
Week 144	1008	[998, 1018]	[925, 1092]		
Week 168	1176	[1166, 1186]	[1093, 1260]		
Week 192	1344	[1334, 1354]	[1261, 1428]		
	< Continues with 24-week intervals >				

Note: If multiple measurements fall within the statistical analysis window, the average of the measurements will be used.

Note that per the protocol Schedule of Assessments, laboratory assessments and vital signs are collected at visits up to Week 48. After Week 48, laboratory assessments are collected per standard of care for clinical management with the following exception: for participants enrolled outside of the US and Europe, hemoglobin and clinical measures of hemolysis (% reticulocytes, absolute reticulocytes, and bilirubin [total, direct, and indirect]) are collected after Week 48 at 24-week intervals (see Section 5.4.3).

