#### **5.3.2.** Adverse Events

Adverse events will be classified according to MedDRA; the most current version at the time of analysis will be used. Severity of adverse events will be graded using the National Cancer Institute Common Terminology Criteria for Adverse Events (NCI CTCAE) version 4.03, when possible, or based on the protocol-specified grading for adverse events not covered in the NCI CTCAE.

Non-SCD-related adverse events and SCD-related adverse events will be summarized separately. SCD-related adverse events include sickle cell anaemia with crisis, acute chest syndrome, pneumonia, priapism, and osteonecrosis. All other adverse events will be considered non-SCD-related.

Summaries of TEAEs, defined as adverse events with an onset on or after the date of informed consent until 28 days after last dose of study drug, will be tabulated by MedDRA system organ class (SOC) and preferred term, as appropriate.

Summaries of TEAEs will be provided for the following categories:

- Non-SCD-related TEAEs
- Non-SCD-related TEAEs by study year
- Non-SCD-related TEAEs by maximum severity
- Non-SCD-related TEAEs assessed as related to study drug by the investigator
- Non-SCD-related TEAEs of rash (group term)
- Non-SCD-related TEAE of abdominal pain (group term)
- Non-SCD-related treatment-emergent serious adverse events (SAEs)
- Non-SCD-related treatment-emergent SAEs by study year
- Non-SCD-related treatment-emergent SAEs assessed as related to study drug by the investigator
- SCD-related TEAEs
- SCD-related TEAEs by study year
- SCD-related TEAEs by maximum severity
- SCD-related TEAEs assessed as related to study drug by the investigator

- SCD-related treatment-emergent SAEs
- SCD-related treatment-emergent SAEs by study year
- SCD-related treatment-emergent SAEs assessed as related to study drug by the investigator
- All TEAEs leading to study drug discontinuation
- All TEAEs leading to study drug dose modification (dose reduction or interruption)

Listings for all adverse events, adverse events leading to study drug discontinuation, SAEs, and deaths will be provided.

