#### **5.3.3.** Clinical Laboratory Assessments

Laboratory abnormalities assessed by the Investigator as clinically significant will be recorded as adverse events.

For participants enrolled in the US and Europe, laboratory values were collected at regular timepoints per the Schedule of Assessments up to Week 48 and analyzed by a central laboratory. After Week 48, laboratory assessments were collected per standard of care for clinical management.

For participants enrolled outside of the US and Europe, laboratory values were collected at regular timepoints per the Schedule of Assessments up to Week 48 and analyzed by each individual site's local laboratory. After Week 48, laboratory assessments were collected per standard of care for clinical management, except for hemoglobin and clinical measures of hemolysis (% reticulocytes, absolute reticulocytes, and bilirubin [total, direct, and indirect]), which continued to be collected every 24 weeks per the Schedule of Assessments.

Descriptive summaries of laboratory parameters (e.g., hematology and serum chemistry) for all participants at baseline and each evaluation post baseline through Week 48, as well as changes from baseline over time, will be provided. If any of the results are below the limit of quantitation or above the limit of quantitation, then the numerical limit will be used in the descriptive summaries.

In addition, laboratory values for hemoglobin and clinical measures of hemolysis collected via local laboratories for participants outside of the US and Europe for all scheduled timepoints (including beyond Week 48) will be summarized descriptively.

Central laboratory values will be graded for selected parameters using the NCI CTCAE. Laboratory abnormality shifts from baseline grade to maximum grade post-baseline up to Week 48 will be tabulated. All assessments after study drug initiation until 28 days after discontinuation of study drug will be included in identifying the maximum grade post-baseline.

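### After Week 48 scheduled laboratory and vital-sign testing largely ends, so the by-study-year non-SCD-related TEAE table is biased toward a fall after Year 1 for the terms those tests detect

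*SAP*

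**What the plan says.** **Findings become adverse events.** Protocol 7.2 says "Clinically significant changes from study baseline in physical examination findings, weight, vital signs, and clinical laboratory parameters, will be recorded as AEs or SAEs". SAP 5.3.3 says "Laboratory abnormalities assessed by the Investigator as clinically significant will be recorded as adverse events". Protocol 7.2.2.3 limits laboratory AEs to abnormalities the Investigator judges clinically significant, and records the diagnosis instead where there is one.

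**Scheduled testing ends.** SAP 3.2 notes that "laboratory assessments and vital signs are collected at visits up to Week 48". The footnotes to Protocol Appendix 1 say "After Week 48, hematology assessments should only be performed per standard of care" and "After Week 48, serum chemistries should only be performed per standard of care". The exception, in Appendix 1 and SAP 5.3.3, is hemoglobin, reticulocytes and bilirubin every 24 weeks for participants outside the US and Europe. In Appendix 1 the every-24-week column is blank for vital signs and for the central laboratory, but marked for adverse events and physical examination. Laboratory tests and vital signs are marked again at End of Study.

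**The tables run over all years.** SAP 5.3.2 lists "Non-SCD-related TEAEs by study year" and "Non-SCD-related treatment-emergent SAEs by study year", plus the two SCD-related counterparts. SAP 3.1 counts study years from consent. SAP 5.3.2 gives no caveat on testing, no separate display of test-detected terms, and no denominator or person-time for the by-year tables. By contrast, SAP 5.3.3 and 5.3.5 stop the general laboratory and vital-sign summaries at Week 48.

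**The concern.** Long-term safety is the study's stated objective, and the by-year tables are where a reader will look for risk changing with time. A preferred term that surfaces only when someone takes a sample or a reading, such as raised ALT, creatinine or blood pressure, depends on how often that is done. If looking becomes less frequent while the true risk stays constant, the recorded count falls. The table would then show improving tolerability where the data show reduced surveillance, and a late laboratory toxicity could be masked in the same way. The step also differs by prior treatment, which is how SAP 4.2 presents results, because the prior placebo and 900 mg groups have extra Week 4 and Week 8 visits in Year 1.

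**Working it through.** **1. Week 48 lies in Study Year 1.** SAP Table 1 gives target day 336 and window 326 to 346. This reproduces: 48 × 7 = 336, ± 10 days. Study Year = ceiling(study day / 365.25): 336/365.25 = 0.92 and 346/365.25 = 0.95, both Year 1. Study day runs from consent and visit day from first dose. The target day therefore stays in Year 1 if consent precedes first dose by up to 365 − 336 = 29 days, and the late edge if by up to 365 − 346 = 19 days. Appendix 1 puts consent and first dose at the same Day 1 visit.

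**2. Scheduled post-baseline assessments per study year, before End of Study.** Visits are Weeks 12, 24 and 48, plus Weeks 4 and 8 after prior placebo or 900 mg. The protocol adds the two early visits for anyone with under 12 weeks of prior treatment.

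| Assessment | Prior group | Year 1 | Each later year |
|---|---|---|---|
| Chemistry, full hematology, vital signs | 1500 mg | 3 | 0 |
| Chemistry, full hematology, vital signs | placebo / 900 mg | 5 | 0 |
| Hemoglobin, reticulocytes, bilirubin, outside US/Europe | 1500 mg | 3 | 2 |
| Hemoglobin, reticulocytes, bilirubin, outside US/Europe | placebo / 900 mg | 5 | 2 |

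**3. What the schedule alone could catch.** Assume a silent abnormality starting on a random day of the year.
- Lasting 4 weeks, Year 1: 5 × 28/365 = 38% (placebo/900 mg) or 3 × 28/365 = 23% (1500 mg).
- Lasting 12 weeks, Year 1: the 84 days before each visit together cover days 1–168 and 253–336 in both groups, so 252/365 = 69%.
- Later years: 0% without an End of Study visit. One on-treatment End of Study visit closing a year would catch 28/365 = 7.7% or 84/365 = 23%.

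**4. Adding standard-of-care tests.** Their frequency is not in the documents, so a range is shown. Assume a constant true rate and detection proportional to the number of looks, with *k* scheduled looks in Year 1.

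*Same standard-of-care frequency s in both years.* Year 2 / Year 1 ratio = s / (k + s):

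| s per year | k = 3 | k = 5 |
|---|---|---|
| 0 | 0 | 0 |
| 2 | 2/5 = 0.40 | 2/7 = 0.29 |
| 4 | 4/7 = 0.57 | 4/9 = 0.44 |
| 12 | 12/15 = 0.80 | 12/17 = 0.71 |

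*Standard of care starts only after Week 48 and replaces the schedule.* Ratio = s / k. Three tests a year give 3/3 = 1.0, no fall, for k = 3 but 3/5 = 0.60 for k = 5, where five a year would be needed. Replacement testing denser than the schedule would reverse the direction (4/3 = 1.33).

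*Hemolysis measures outside the US and Europe.* Ratio = (2 + s) / (k + s). For s = 0 to 4 this is 2/3 = 0.67 to 6/7 = 0.86 (k = 3), or 2/5 = 0.40 to 6/9 = 0.67 (k = 5).

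**5. Effect on the TEAE total.** If a share *f* of TEAEs is test-detected, the artefactual fall in the total is f × (1 − ratio). Taking ratios 0 to 0.57, f = 5% gives 5.0% down to 2.2%, and f = 20% gives 20% down to 8.6%. The documents do not give *f*.

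**The case against.** The strongest reply is that testing does not stop. Laboratory assessments continue per standard of care, extra assessments are allowed, and any clinically significant finding is an AE whichever test found it. This stands. A reader might infer that the fall is built into the tables and equals 100%. The documents do not support that, because 100% is the case with no standard-of-care testing at all. Equally, no provision requires such testing to replace the schedule, and at equal frequency in both years a fall remains even at 12 tests a year.

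End of Study repeats the tests, and participants who complete per protocol stay on drug until that visit. This also stands, but it is one look per participant. For early withdrawals the visit is 28 to 35 days after last dose, while the SAP's TEAE period closes at 28 days, so a finding dated to that visit mostly falls outside it.

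Only clinically significant findings become AEs, so many brief silent abnormalities would be recorded in no year. That limits the effect on the total, though not the direction for the terms that are recorded.

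A reader might also extend the point to all four by-year tables. That goes too far. The SCD-related tables cover crisis, acute chest syndrome, pneumonia, priapism and osteonecrosis, none of which is a laboratory or vital-sign term. Most SAE criteria are clinical outcomes, and AE enquiry continues every 24 weeks. The explicit laboratory-defined SAE route is a potential Hy's law case (Protocol 7.2.2.3).

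Finally, the SAP states the Week 48 cutoff and tabulates by system organ class, so Investigations terms already sit together. But the cutoff is not carried into SAP 5.3.2, and terms such as hyperkalaemia or hypertension fall outside that class.

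**Conclusion.** The point holds for laboratory- and vital-sign-detected terms in the non-SCD-related by-study-year TEAE table. Scheduled post-baseline looks drop from 5 or 3 in Year 1 to 0 per later year before End of Study, or to 2 for hemolysis measures outside the US and Europe. Those terms are therefore biased toward a fall, and time trend is confounded with surveillance.

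The size cannot be fixed from the documents. It runs from no fall, if standard-of-care testing fully replaces the schedule, to 100% if there is none. The illustrative ratios of 0.29 to 0.80 assume a constant true rate, detection proportional to looks, and 2 to 12 standard-of-care tests a year in both years. The effect on total TEAEs depends on the unstated share that is test-detected. The effect on SAEs is mainly confined to laboratory-defined cases. Symptom-detected events and the SCD-related by-year tables are not affected by this mechanism. The change is worth making because these tables serve the study's main purpose and the correction is cheap.

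**What to change.** Amend SAP 5.3.2 for the non-SCD-related by-study-year TEAE table and, for laboratory-defined SAEs only, the non-SCD-related by-study-year SAE table:

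- Show laboratory- and vital-sign-defined preferred terms in a separate panel: the Investigations class plus a short prespecified list (for example hyperkalaemia and hypertension).
- Give participants at risk and person-time for each study year.
- Present counts up to the Week 48 visit separately from later counts.
- State that the later counts are not comparable with Year 1 because scheduled testing had ended, noting the continued hemolysis measures outside the US and Europe.
- Use the number of participants tested as a denominator only where the tests are in the database. The documents do not establish that all standard-of-care tests, especially vital signs, are captured.

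The cost is SAP wording, a term list and one extra panel per affected table. The tables become slightly longer and the term list needs some judgement, so it should be fixed before the final analysis. Study conduct and data collection do not change.

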#### **5.3.3.** Clinical Laboratory Assessments

Laboratory abnormalities assessed by the Investigator as clinically significant will be recorded as adverse events.

For participants enrolled in the US and Europe, laboratory values were collected at regular timepoints per the Schedule of Assessments up to Week 48 and analyzed by a central laboratory. After Week 48, laboratory assessments were collected per standard of care for clinical management.

For participants enrolled outside of the US and Europe, laboratory values were collected at regular timepoints per the Schedule of Assessments up to Week 48 and analyzed by each individual site's local laboratory. After Week 48, laboratory assessments were collected per standard of care for clinical management, except for hemoglobin and clinical measures of hemolysis (% reticulocytes, absolute reticulocytes, and bilirubin [total, direct, and indirect]), which continued to be collected every 24 weeks per the Schedule of Assessments.

Descriptive summaries of laboratory parameters (e.g., hematology and serum chemistry) for all participants at baseline and each evaluation post baseline through Week 48, as well as changes from baseline over time, will be provided. If any of the results are below the limit of quantitation or above the limit of quantitation, then the numerical limit will be used in the descriptive summaries.

In addition, laboratory values for hemoglobin and clinical measures of hemolysis collected via local laboratories for participants outside of the US and Europe for all scheduled timepoints (including beyond Week 48) will be summarized descriptively.

Central laboratory values will be graded for selected parameters using the NCI CTCAE. Laboratory abnormality shifts from baseline grade to maximum grade post-baseline up to Week 48 will be tabulated. All assessments after study drug initiation until 28 days after discontinuation of study drug will be included in identifying the maximum grade post-baseline.

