7.1.5. Laboratory Assessments

Central laboratory assessments will be performed for participants enrolled in the United States and Europe.

Local laboratory assessments will be performed by each site's local laboratory for participants enrolled outside of the United States or Europe.

The laboratory parameters listed in the sections below will be assessed. Additional laboratory assessments may be collected as indicated per standard of care for clinical management.

For adolescent participants, the total volume of blood collected for will not exceed the recommended blood sample volume limits outlined in 2010 WHO Guidelines. For this study, 12 years of age is the youngest age to be enrolled, thus total blood volume collection will not exceed 2.4 mL/kg in a given 4 week period, for any adolescent enrolled in the study.

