10.2. Laboratory Accreditation

The laboratory facility used for analysis of clinical laboratory samples must provide evidence of adequate licensure or accreditation. Copies of laboratory certification, licensure, and reference ranges (as appropriate) will be supplied to the Sponsor prior to study initiation. The

Sponsor or designee should be notified of any changes in reference range values or certification/license renewal during the course of the study.

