# **4.2.** Safety Population

The safety population includes all enrolled participants who received treatment with study drug (voxelotor) during Study GBT440-034.

The safety population will be the primary analysis population for this study.

Analyses will be presented for overall population, and by prior treatment group (i.e., placebo, voxelotor 900 mg, and voxelotor 1500 mg) based on treatment received in the parent study GBT440-031, as appropriate.

<sup>a Including Week 72, End of Treatment, or End of Study laboratory values collected in Study GBT440-031.

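### The laboratory shift table grades central values only, so it omits participants outside the US and Europe, although safety summaries are meant to cover everyone treated

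*SAP*

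**What the plan says.** SAP section 5.3.3 sets out the graded analysis in two consecutive sentences: "Central laboratory values will be graded for selected parameters using the NCI CTCAE", and then "Laboratory abnormality shifts from baseline grade to maximum grade post-baseline up to Week 48 will be tabulated". It names no other source of laboratory grades.

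The Protocol decides by region who has central values. Section 7.1.5 says "Central laboratory assessments will be performed for participants enrolled in the United States and Europe" and "Local laboratory assessments will be performed by each site's local laboratory for participants enrolled outside of the United States or Europe". The row in the Appendix 1 schedule reads "Hematology/Chemistry analyzed by Central Laboratory (US and Europe only", with a separate local-laboratory row for everyone else. SAP 5.3.3 repeats the same regional split for scheduled testing up to Week 48.

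On population, SAP section 5.3 bases the safety summaries on the safety population. Section 4.2 defines that as all enrolled participants who received voxelotor in this study, with no regional limit, and adds: "The safety population will be the primary analysis population for this study". Protocol section 8.1.1.1 likewise applies the safety analysis to all enrolled participants.

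On local laboratories, Protocol section 10.2 says: "Copies of laboratory certification, licensure, and reference ranges (as appropriate) will be supplied to the Sponsor prior to study initiation". It also asks that the sponsor be told when ranges change.

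**The concern.** The restriction is one word, central, in one sentence. Through the Protocol's regional split, that word becomes an exclusion of participants by geography. The SAP gives no reason for it and does not reconcile it with section 5.3.

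What is at stake is the one planned laboratory output that takes each participant's worst post-baseline grade and sets it against the baseline grade, without depending on anyone's judgement of clinical significance. A graded shift in a participant outside the US and Europe would be missing from that table. The table's percentages would describe the centrally tested participants, not the safety population.

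**Working it through.** The plan states no figure for this analysis, so there is nothing to reproduce. The check is a reading of the text, followed by an illustration of size.

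**Step 1: who can be graded.**
- Grades come from central values (SAP 5.3.3).
- Central values exist for US and European participants (Protocol 7.1.5, Appendix 1, SAP 5.3.3).
- Neither document provides for grading local values, or for central testing of samples from elsewhere.
- A shift needs a post-baseline grade. SAP section 3.1 allows a baseline carried over from GBT440-031, but that supplies a baseline only and would not bring these participants into the table.

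So a participant outside the US and Europe contributes nothing to the shift table.

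**Step 2: what still covers these participants.**
- *Ungraded descriptive summaries through Week 48, for all participants (SAP 5.3.3).* SAP section 3.2 averages multiple measurements within an analysis window, and the windows are wide. The Week 48 window runs from treatment day 253 to 420, which is 420 − 253 + 1 = 168 days. When a window holds more than one value, the minimum and maximum reported at that timepoint are extremes of averages, so a brief peak can be diluted.
- *Hemoglobin and hemolysis measures beyond Week 48 (SAP 5.3.3).* These do not include ALT, creatinine, platelets or white cells.
- *Laboratory adverse events, including those leading to dose modification or discontinuation, and SAE reports of potential Hy's law cases (Protocol 7.2.2.3, SAP 5.3.2).* Except for Hy's law cases, which have laboratory thresholds, recording depends on the investigator judging the abnormality clinically significant.
- *Listings of out-of-range and clinically significant values (Protocol 8.1.1.1).* SAP 5.3.3 does not mention them. They are listings, not tabulated shifts.

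None of these is a systematic table of baseline grade against maximum grade.

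**Step 3: illustrative size.**

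Inputs: N = 274, the upper limit on sample size in SAP section 2.3, and f, the share outside the US and Europe. The documents do not give f, so it is assumed. The graded number is n = 274 × (1 − f). Two quantities follow:
- one-sided 95% upper bound when no events are seen: 1 − 0.05^(1/n)
- chance of seeing at least one abnormality whose true frequency is 1%: 1 − 0.99^n

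| f (assumed) | Graded n | Not graded | Zero-event upper bound | Chance of at least one event at 1% |
|---|---|---|---|---|
| 0% | 274 | 0 | 1.1% | 93.6% |
| 10% | 247 | 27 | 1.2% | 91.6% |
| 25% | 206 | 68 | 1.4% | 87.4% |
| 50% | 137 | 137 | 2.2% | 74.8% |
| 75% | 68 | 206 | 4.3% | 49.5% |

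For example, at f = 50%, 1 − 0.05^(1/137) = 0.0216 and 1 − 0.99^137 = 0.748.

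**The case against.** The strongest reply has four parts.

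**Other analyses retain these participants.** A reader might infer that a laboratory signal outside the US and Europe would go unseen altogether. The documents do not support that, because the summaries, adverse events and SAEs in Step 2 all include these participants. This part stands and limits the point to the graded table. It does not make the table complete, because those routes average within windows, depend largely on investigator judgement, or are listings.

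**No Protocol commitment is broken.** Protocol 8.1.1.1 promises summaries of change, flags and a list of clinically significant values. It does not promise a graded shift table, which is an SAP addition. That is right. The conflict is within the SAP, between 5.3.3 and the population stated in 5.3, and with the Protocol's general statement that safety analysis covers everyone enrolled.

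**The table may be labelled correctly.** SAP section 6 places the mock-ups in a separate document, so it cannot be said that the table will be presented as the whole trial's result. Nor can it be said which toxicities it covers, since the SAP refers only to selected parameters. Both cautions stand.

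**One standardised laboratory is a defensible basis for grading.** Local ranges differ, and Protocol 10.2 asks for them only as appropriate, so some may be missing. This is a fair reason to show the two sources separately. It is a weak reason to leave one out without comment, since the SAP already summarises laboratory values for all participants, central and local. The Protocol's ALT rules are also expressed as multiples of the upper limit of normal with no regional distinction, so sites that rely on local testing must already read results against a local limit.

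**Conclusion.** The point holds for the CTCAE-graded values and the shift table, and no further. As written, SAP 5.3.3 excludes every participant outside the US and Europe from the only systematic maximum-grade table, in conflict with SAP 5.3 and with no reason given.

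The exclusion follows from the text and needs no assumption. Its size cannot be determined, because the documents do not give enrolment by region. With 25% to 50% outside the US and Europe, the zero-event bound would move from about 1.1% to between 1.4% and 2.2%: modest at the lower share, about double at the higher. These figures use the cap of 274, not an actual safety-population count. The bound is a gauge of lost information; the plan is descriptive and does not include it.

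This should be corrected before the final analysis. It does not undermine the rest of the laboratory safety reporting.

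**What to change.** Amend SAP 5.3.3 as follows:
- Grade the selected parameters for both central and local values, using each laboratory's own reference limits.
- Present shifts from baseline to maximum grade for the full safety population, and separately by laboratory source (central, local), with the graded denominator shown for each parameter.
- Where a local reference range is unavailable, grade only those selected parameters whose grade limits are absolute values, and report how many participants could not be graded.

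If the sponsor prefers to keep central values only, the least that is needed is to state the restriction, its reason and the graded denominator in the SAP and in the table title.

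The local results are already collected and already used in the ungraded summaries. The cost is linking local ranges, including changes over time, to the results, plus one further table split. The downside is variation between local ranges, which the split by source makes visible.
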